#### Arm E

Participant Identifier:	Protocol #: MCC-20-COVID-01-PMC		
Doctor: [name] [name]			
Doctor: [name] [name]			
Nurse: enter name and phone number			
You will take the following number of capsules/tablets each time (per dose) as listed in the table below:			
Study Botanical Product Name	dose	# of times/doses each day	Approximate time to take tea or coffee
Artemisia annua	1 pod or 2 tea bags	3 times per day	___:___  a.m. ___:___  p.m. :  p.m.

Day	Date	Number of Artemisia annua tea bag or pod	Time of Dose	Number of Artemisia annua tea bag or pod	Time of Dose	Number of Artemisia annua tea bag or pod	Time of Dose
1		-	___:___  a.m.  Dose not taken Why: _____	-	___:___  p.m.  Dose not taken Why: _____	-	___:___  p.m.  Dose not taken Why: _____
2		-	___:___  a.m.  Dose not taken Why: _____	-	___:___  p.m.  Dose not taken Why: _____	-	___:___  p.m.  Dose not taken Why: _____
3		-	___:___  a.m.  Dose not taken Why: _____	-	___:___  p.m.  Dose not taken Why: _____	-	___:___  p.m.  Dose not taken Why: _____
4		-	___:___  a.m.  Dose not taken Why: _____	-	___:___  p.m.  Dose not taken Why: _____	-	___:___  p.m.  Dose not taken Why: _____

5		-	____:____  a.m.  Dose not taken Why: _____	-	____:____  p.m.  Dose not taken Why: _____	-	____:____  p.m.  Dose not taken Why: _____
6		-	____:____  a.m.  Dose not taken Why: _____	-	____:____  p.m.  Dose not taken Why: _____	-	____:____  p.m.  Dose not taken Why: _____
7		-	____:____  a.m.  Dose not taken Why: _____	-	____:____  p.m.  Dose not taken Why: _____	-	____:____  p.m.  Dose not taken Why: _____
8		-	____:____  a.m.  Dose not taken Why: _____ _____	-	____:____  p.m.  Dose not taken Why: _____ _____	-	____:____  p.m.  Dose not taken Why: _____ _____
9		-	____:____  a.m.  Dose not taken Why: _____ _____	-	____:____  p.m.  Dose not taken Why: _____ _____	-	____:____  p.m.  Dose not taken Why: _____ _____
10		-	____:____  a.m.  Dose not taken Why: _____	-	____:____  p.m.  Dose not taken Why: _____	-	____:____  p.m.  Dose not taken Why: _____
11		-	____:____  a.m.  Dose not taken Why: _____	-	____:____  p.m.  Dose not taken Why: _____	-	____:____  p.m.  Dose not taken Why: _____
12		-	____:____  a.m.  Dose not taken Why: _____	-	____:____  p.m.  Dose not taken Why: _____	-	____:____  p.m.  Dose not taken Why: _____
13		-	____:____  a.m.  Dose not taken Why: _____	-	____:____  p.m.  Dose not taken Why: _____	-	____:____  p.m.  Dose not taken Why: _____
14		-	____:____  a.m.  Dose not taken Why: _____ _____	-	____:____  p.m.  Dose not taken Why: _____ _____	-	____:____  p.m.  Dose not taken Why: _____ _____

Participant/Caregiver Signature: \_\_\_\_\_  
 Date: \_\_\_\_\_

*IMP: Artemisia annua, Artesunate, Camostat mesilate, Ivermectin,  
Study #: MCC-20-COVID-01-PMC  
Amendment 4 August 28, 2020*

FOR STUDY TEAM USE ONLY	
Staff Initials:	
Date Dispensed:	Date Returned:
# pills/caps/tabs dispensed:	# pills/caps/tabs returned:
# pills/caps/tabs that should have been taken:	
Discrepancy Notes:	

### Study Participant Self-Administration Study Drug Diary

Please record the number of times you drink the Artesunate tea or coffee, the time you take them and any comments below and bring the completed Diary as well as your study tea or coffee supply, to your next study visit. This will help us keep track of your study drug and how well you are tolerating it.

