#### 8.1.5 *Artemisia annua* tea and coffee

### Procurement

**Outpatients:** Coffee and tea botanical products will be directly shipped overnight to study patients, who are outpatients by Baesman on behalf of ArtemiLife. Patients without a pod coffee maker will also receive a coffee maker.

The distributor for *Artemisia annua* is as follows:

Baesman Distributors

[name]

[name]

Contact: [[contact]](mailto:[contact])

Subjects randomized to Arm E will have their information entered into the ordering portal of

*IMP: Artemisia annua, Artesunate, Camostat mesilate, Ivermectin,  
Study #: MCC-20-COVID-01-PMC  
Amendment 4 August 28, 2020*

Baesman Distributors website.

**Inpatients:** This botanical product will be dispensed by Artemilife to the IDS pharmacy.

Formulation

Decaf coffee: 450 mg per pod

Tea: 225 mg per bad

Preparation, Storage and Stability

Tea and coffee should be stored at room temperature.

Coffee: Dispense 42, 450 mg pods

Tea: Dispense 84, 225 mg bags

Administration

Refer to the treatment section for specific administration instructions

Patients should be instructed to brew 1 (450mg) coffee pod or 2 (225mg) tea bags in 8 oz of water three times per day Days 1-14.

Drug Interactions

Increased Effect/Toxicity: No known drug interactions

Decreased Effect: CYP2A6 strong inducers may reduce the effects of Artemisia annua

Herb/Nutraceutical Interactions: No known interactions

Pharmacokinetics

Absorption: well absorbed orally

Distribution: Not established

Metabolism: Metabolized by CYP2A6

Half-life elimination: 1hr

Terminal: Not reported

Excretion: Not known

Adverse Events

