#### Arm F

Participant Identifier:	Protocol #: MCC-20-COVID-01-PMC		
Doctor: [name] [name]			
Doctor: [name] [name]			
Nurse: enter name and phone number			
You will take the following number of capsules/tablets each time (per dose) as listed in the table below:			
Study Drug Name	dose	# of times/doses each day	Approximate time to take drug
Artesunate	1 pod or 2 tea bags	3 times per day	__:__  a.m. __:__  p.m. :  p.m.

Day	Date	Number of Artesunate tea bag or pod	Time of Dose	Number of Artesunate tea bag or pod	Time of Dose	Number of Artesunate tea bag or pod	Time of Dose
1		–	__:__  a.m.  Dose not taken Why: _____	–	__:__  p.m.  Dose not taken Why: _____	–	__:__  p.m.  Dose not taken Why: _____
2		–	__:__  a.m.  Dose not taken Why: _____	–	__:__  p.m.  Dose not taken Why: _____	–	__:__  p.m.  Dose not taken Why: _____
3		–	__:__  a.m.  Dose not taken Why: _____	–	__:__  p.m.  Dose not taken Why: _____	–	__:__  p.m.  Dose not taken Why: _____
4		–	__:__  a.m.  Dose not taken Why: _____	–	__:__  p.m.  Dose not taken Why: _____	–	__:__  p.m.  Dose not taken Why: _____

5		-	____:____  a.m.  Dose not taken Why: _____	-	____:____  p.m.  Dose not taken Why: _____	-	____:____  p.m.  Dose not taken Why: _____
6		-	____:____  a.m.  Dose not taken Why: _____	-	____:____  p.m.  Dose not taken Why: _____	-	____:____  p.m.  Dose not taken Why: _____

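### The Arm F (artesunate) diary in Appendix C prints the Arm E tea/coffee dose and three-times-daily schedule, contradicting the regimen of two tablets once daily

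*Combined protocol and SAP*

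**What the plan says.** **The Arm F diary (Appendix C).** The opening instruction reads "Please record the number of times you drink the Artesunate tea or coffee", and the patient is asked to bring the diary "as well as your study tea or coffee supply, to your next study visit". A lead-in line above the dose table tells the patient that the table lists the number of capsules or tablets to take at each dose. The table names artesunate, gives the dose as "1 pod or 2 tea bags" and the frequency as "3 times per day". The recording grid has three columns per day headed "Number of Artesunate tea bag or pod", for Days 1 to 14.

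**The Arm F regimen.** Two places state it in full. The Arm F table in Section 6.1 and the administration instruction in Section 8.1.6 both give two tablets once a day on Days 1 to 14. Three others are consistent with it without each stating it. Section 2.5 gives 200 mg orally per day for 14 days, the formulation entry in Section 8.1.6 gives a 100 mg tablet, and the dispensing entry there gives 28 tablets.

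**How the page is used.** Section 4.9 has medication, diary and instructions handed out together on Day 1, and medication and diary collected at Day 14.

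**The concern.** No artesunate tea, coffee pod or tea bag exists in this trial, so the page describes a product the patient does not have. It is also more than a log: the lead-in line makes the table a dosing instruction, and three times daily is the only frequency printed on the page. A patient holding a bottle of tablets could discount the reference to pods and still follow the frequency.

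Two things are at stake. One is a daily dose and treatment duration that differ from the plan in some Arm F patients. The other is the record: entries would be made under tea-bag or pod headings, and the return line asks for tea or coffee, where the Arm C and Arm D tablet diaries ask for the drug supply and empty bottles. Compliance with each regimen is a secondary objective (Section 1.2.6), so it is fair to ask whether that objective is affected.

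**Working it through.** **Step 1. Reproduce the plan's own figure.** Inputs from Sections 6.1 and 8.1.6: 2 tablets per dose, 1 dose per day, 14 days, 100 mg per tablet.

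- Tablets: 2 × 1 × 14 = 28, which matches the 28 dispensed.
- Supply: 28 × 100 mg = 2,800 mg. Planned total: 14 × 200 mg = 2,800 mg. The two are equal.

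**Step 2. Compute the supply that the Arm F diary implies.** Inputs from the Arm F page: 1 pod or 2 bags per dose, 3 doses per day, 14 days.

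- Pods: 1 × 3 × 14 = 42.
- Bags: 2 × 3 × 14 = 84.

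Section 8.1.5 dispenses exactly these amounts for Arm E: "Coffee: Dispense 42, 450 mg pods" and "Tea: Dispense 84, 225 mg bags". The schedule printed for Arm F is therefore the Arm E schedule.

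**Step 3. Compare the two diary pages.** The Arm E grid is headed "Number of Artemisia annua tea bag or pod" and the Arm F grid carries the same heading with the product name exchanged. The opening instruction, return line, dose cell, frequency cell and three-column layout also match. An error that recurs in all these places and down all 14 rows is not a PDF-reading artefact.

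**Step 4. Compare the layouts.** Diary slots: 3 × 14 = 42. Planned doses: 1 × 14 = 14. This describes the form only.

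**Step 5. What following the printed frequency could mean.** The form gives no tablets-per-dose figure, so the number per dose is an assumption:

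| Assumed tablets, three times daily | mg per day | Ratio to 200 mg | Days until 28 tablets run out |
|---|---|---|---|
| 1 | 3 × 100 = 300 | 1.5 | 28 / 3 = 9.3 |
| 2 | 6 × 100 = 600 | 3.0 | 28 / 6 = 4.7 |

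In both rows the total from one dispensing stays at 2,800 mg. The daily dose would be higher and the course shorter.

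**The case against.** The strongest reply is that the page is so plainly misapplied that a patient with tablets would ignore it or ask, and that other safeguards cover the dose. A physician prescribes according to Section 6 and the investigational pharmacy dispenses (Section 8.1.1). Section 8.1.6 says what patients should be told, and the supply is limited to 28 tablets. There are contacts at Day 3 or 4, Day 7 and Day 10 or 11, and medication is collected at Day 14 (Section 4.9).

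Much of this stands. The supply limit caps total exposure, and the prescribing and dispensing route follows the correct regimen. But none of it corrects the page. The content of the instructions handed out on Day 1 is not given. The interim contacts are described as covering clinical status, questions and toxicity, with no stated dosing check. A count of returned tablets shows the total taken, not the daily pattern.

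A second reply concerns compliance, and it succeeds. Section 12.2 records compliance on case report forms and does not name the diary as the source. Drug accountability runs separately under Sections 8.1.1 and 8.1.2, and the staff block of the diary itself counts tablets dispensed and returned. The cells in the grid are blank and timed, so a once-daily dose can still be entered.

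**Conclusion.** The contradiction is certain and lies in the current text: the patient-facing Arm F page states the wrong product form and three times the planned frequency, and nothing else in the documents corrects it. It should be fixed. The consequence is a possible wrong-frequency risk of unknown likelihood, plus mislabelled diary entries if the form is used.

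A reader might infer more, and the documents do not support it:

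- **That patients would take 300 or 600 mg per day.** Both figures rest on an assumed number of tablets per dose.
- **That exposure would triple.** From one dispensing the total cannot exceed 2,800 mg.
- **That a correctly dosed patient would score 14/42, or 33%, compliance.** The plan gives no compliance formula and does not use the diary slots as a denominator.
- **That the compliance objective is compromised.** This is not shown, given the case report forms and tablet counts.
- **That patients have been misdosed.** The documents do not show that anyone has received the form.

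The primary analysis in Section 9.5 is unaffected. Its population is patients randomized who took at least one dose, its endpoint is the ordinal scale, and neither depends on the diary schedule. The sample size does not change.

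**What to change.** Replace the Arm F page with a tablet diary that states two 100 mg tablets once daily, has one recording column per day for Days 1 to 14, and asks the patient to return the tablet supply and empty bottles.

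The once-daily Arm C diary is a convenient layout, but it needs three changes. Remove its meal timing, which belongs to ivermectin (Section 8.1.3) and has no counterpart in the artesunate sections. Extend its two day rows to 14. Pre-fill two tablets where Arm C leaves the count blank for weight-based dosing.

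If the present form has already been given to any patient, ask about and document actual intake at a contact already scheduled.

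The cost is one corrected page, review of the changed form under Section 13.1 if it is not classed as administrative, and a brief intake check for any patient already given the present form. No patients, visits or procedures are added.

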#### Arm F

Participant Identifier:	Protocol #: MCC-20-COVID-01-PMC		
Doctor: [name] [name]			
Doctor: [name] [name]			
Nurse: enter name and phone number			
You will take the following number of capsules/tablets each time (per dose) as listed in the table below:			
Study Drug Name	dose	# of times/doses each day	Approximate time to take drug
Artesunate	1 pod or 2 tea bags	3 times per day	__:__  a.m. __:__  p.m. :  p.m.

Day	Date	Number of Artesunate tea bag or pod	Time of Dose	Number of Artesunate tea bag or pod	Time of Dose	Number of Artesunate tea bag or pod	Time of Dose
1		–	__:__  a.m.  Dose not taken Why: _____	–	__:__  p.m.  Dose not taken Why: _____	–	__:__  p.m.  Dose not taken Why: _____
2		–	__:__  a.m.  Dose not taken Why: _____	–	__:__  p.m.  Dose not taken Why: _____	–	__:__  p.m.  Dose not taken Why: _____
3		–	__:__  a.m.  Dose not taken Why: _____	–	__:__  p.m.  Dose not taken Why: _____	–	__:__  p.m.  Dose not taken Why: _____
4		–	__:__  a.m.  Dose not taken Why: _____	–	__:__  p.m.  Dose not taken Why: _____	–	__:__  p.m.  Dose not taken Why: _____

5		-	____:____  a.m.  Dose not taken Why: _____	-	____:____  p.m.  Dose not taken Why: _____	-	____:____  p.m.  Dose not taken Why: _____
6		-	____:____  a.m.  Dose not taken Why: _____	-	____:____  p.m.  Dose not taken Why: _____	-	____:____  p.m.  Dose not taken Why: _____
7		-	____:____  a.m.  Dose not taken Why: _____	-	____:____  p.m.  Dose not taken Why: _____	-	____:____  p.m.  Dose not taken Why: _____
8		-	____:____  a.m.  Dose not taken Why: _____	-	____:____  p.m.  Dose not taken Why: _____	-	____:____  p.m.  Dose not taken Why: _____
9		-	____:____  a.m.  Dose not taken Why: _____	-	____:____  p.m.  Dose not taken Why: _____	-	____:____  p.m.  Dose not taken Why: _____
10		-	____:____  a.m.  Dose not taken Why: _____	-	____:____  p.m.  Dose not taken Why: _____	-	____:____  p.m.  Dose not taken Why: _____
11		-	____:____  a.m.  Dose not taken Why: _____	-	____:____  p.m.  Dose not taken Why: _____	-	____:____  p.m.  Dose not taken Why: _____
12		-	____:____  a.m.  Dose not taken Why: _____	-	____:____  p.m.  Dose not taken Why: _____	-	____:____  p.m.  Dose not taken Why: _____
13		-	____:____  a.m.  Dose not taken Why: _____	-	____:____  p.m.  Dose not taken Why: _____	-	____:____  p.m.  Dose not taken Why: _____
14		-	____:____  a.m.  Dose not taken Why: _____	-	____:____  p.m.  Dose not taken Why: _____	-	____:____  p.m.  Dose not taken Why: _____

[figure not shown]
Participant/Caregiver Signature: \_\_\_\_\_  
 Date: \_\_\_\_\_

*IMP: Artemisia annua, Artesunate, Camostat mesilate, Ivermectin,  
Study #: MCC-20-COVID-01-PMC  
Amendment 4 August 28, 2020*

FOR STUDY TEAM USE ONLY	
Staff Initials:	
Date Dispensed:	Date Returned:
# pills/caps/tabs dispensed:	# pills/caps/tabs returned:
# pills/caps/tabs that should have been taken:	
Discrepancy Notes:	

[figure not shown]
*IMP: Artemisia annua, Artesunate, Camostat mesilate, Ivermectin,  
Study #: MCC-20-COVID-01-PMC  
Amendment 4 August 28, 2020*

## APPENDIX D: TELEHEALTH TRIAGE AND DRIVE/THROUGH WALK-IN ENROLLMENT

[figure not shown]
**APPENDIX E: GETWELL LOOP/CENTRALIZED COVID-19 TELEHEALTH AT UK (CTU) ALGORITHM**

[figure not shown]
## APPENDIX F: CURRENT RECRUITMENT STRATEGY AND SCHEMATIC FOR INTAKE AND CONSENT FOR RESEARCH AT RESEARCH DESIGNATED CLINIC

### Proposed Patient Recruitment for COVID-19 Research:

- Multiple patient streams referred to centralized research unit
- Research unit has established COVID-19 protocols
- Creates synergy to maximize recruitment into studies – minimized competition
- Can advertise one site for research referral or to direct interested patients
- Takes advantage of existing relationship with patient referral streams and CCTS biobank to create streamlined process, avoiding duplicated efforts, and lost opportunities for recruitment

### PATIENT FLOW FOR INTAKE INTO ID CLINIC

## APPENDIX G: TOXICITY GRADING SCALES FOR DETERMINING SEVERITY OF ADVERSE EVENTS

<https://www.niaid.nih.gov/research/dmid-safety-reporting-pharmacovigilance>

### ADULT TOXICITY TABLES

**ABBREVIATIONS:** Abbreviations utilized in the Table:

ULN = Upper Limit of Normal LLN = Lower Limit of Normal

Rx = Therapy Req = Required

Mod = Moderate IV = Intravenous

ADL = Activities of Daily Living Dec = Decreased

### **ESTIMATING SEVERITY GRADE**

For abnormalities NOT found elsewhere in the Toxicity Tables use the scale below to estimate grade of severity:

GRADE 1 Mild	Transient or mild discomfort (< 48 hours); no medical intervention/therapy required
GRADE 2 Moderate	Mild to moderate limitation in activity - some assistance may be needed; no or minimal medical intervention/therapy required
GRADE 3 Severe	Marked limitation in activity, some assistance usually required; medical intervention/therapy required, hospitalizations possible
GRADE 4 Life-threatening	Extreme limitation in activity, significant assistance required; significant medical intervention/therapy required, hospitalization or hospice care probable

### **SERIOUS OR LIFE-THREATENING AEs**

ANY clinical event deemed by the clinician to be serious or life-threatening should be considered a grade 4 event. Clinical events considered to be serious or life-threatening include, but are not limited to seizures, coma, tetany, diabetic ketoacidosis, disseminated intravascular coagulation, diffuse petechiae, paralysis, acute psychosis, severe depression.

HEMATOLOGY				
	Grade 1	Grade 2	Grade 3	Grade 4
Hemoglobin	9.5-10.5 g/dL	8.0-9.4 g/dL	6.5-7.9 g/dL	<6.5 g/dL
Absolute Neutrophil Count	1000-1500/mm 	750-999/mm 	500-749/mm 	<500/mm 
Platelets	75,000-99,999/mm 	50,000-74,999/mm 	20,000-49,999/mm 	<20,000/mm 
WBCs	>13,000/mm 	13,000-15,000/mm 	15,000-30,000/mm 	>30,000 or <1,000/mm 
Polymorphonuclear Leucocytes + Band Cells	>80%	90-95%	>95%	-----
Abnormal Fibrinogen	Low: 100-200 mg/dL High: 400-600 mg/dL	Low: <100 mg/dL High: >600 mg/dL	Low: <50 mg/dL -----	Fibrinogen associated with gross bleeding or with disseminated coagulation
Fibrin Split Product	20-40 µg/mL	41-50 µg/mL	51-60 µg/mL	>60 µg/mL
Prothrombin Time (PT)	1.01-1.25 × ULN	1.26-1.5 × ULN	1.51-3.0 × ULN	>3 × ULN
Activated Partial Thromboplastin (APPT)	1.01-1.66 × ULN	1.67-2.33 × ULN	2.34-3 × ULN	>3 × ULN
Methemoglobin	5.0-9.9%	10.0-14.9%	15.0-19.9%	>20.0%

CHEMISTRIES				
	Grade 1	Grade 2	Grade 3	Grade 4
Hyponatraemia	130-135 mEq/L	123-129 mEq/L	116-122 mEq/L	< 116 mEq/L or abnormal sodium with mental status changes or seizures
Hypernatraemia	146-150 mEq/L	151-157 mEq/L	158-165 mEq/L	> 165 mEq/L or abnormal sodium with mental status changes or seizures
Hypokalaemia	3.0 - 3.4 mEq/L	2.5 - 2.9 mEq/L	2.0 - 2.4 mEq/L or intensive replacement therapy or hospitalization required	< 2.0 mEq/L or abnormal potassium with paresis, ileus or life-threatening arrhythmia
Hyperkalaemia	5.6 - 6.0 mEq/L	6.1 - 6.5 mEq/L	6.6 - 7.0 mEq/L	> 7.0 mEq/L or abnormal potassium with life-threatening arrhythmia
Hypoglycaemia	55-64 mg/dL	40-54 mg/dL	30-39 mg/dL	<30 mg/dL or abnormal glucose with mental status changes or coma
Hyperglycaemia (non-fasting and no prior diabetes)	116 - 160 mg/dL	161- 250 mg/dL	251 - 500 mg/dL	> 500 mg/dL or abnormal glucose with ketoacidosis or seizures
Hypocalcaemia (corrected for albumin)	8.4 - 7.8 mg/dL	7.7 - 7.0 mg/dL	6.9 - 6.1 mg/dL	< 6.1 mg/dL or abnormal calcium with life threatening arrhythmia or tetany
Hypercalcaemia (correct for albumin)	10.6 - 11.5 mg/dL	11.6 - 12.5 mg/dL	12.6 - 13.5 mg/dL	> 13.5 mg/dL or abnormal calcium with life-threatening arrhythmia
Hypomagnesaemia	1.4 - 1.2 mEq/L	1.1 - 0.9 mEq/L	0.8 - 0.6 mEq/L	< 0.6 mEq/L or abnormal magnesium with life-threatening arrhythmia
Hypophosphataemia	2.0 - 2.4 mg/dL	1.5 -1.9 mg/dL or replacement Rx required	1.0 -1.4 mg/dL intensive therapy or hospitalization required	< 1.0 mg/dL or abnormal phosphate with life-threatening arrhythmia
Hyperbilirubinaemia	1.1 - 1.5 x ULN	1.6 - 2.5 x ULN	2.6 - 5 x ULN	> 5 x ULN
BUN	1.25 - 2.5 x	2.6 - 5 x ULN	5.1 - 10 x ULN	> 10 x ULN

CHEMISTRIES				
	Grade 1	Grade 2	Grade 3	Grade 4
Hyperuricaemia (uric acid)	7.5 – 10.0 mg/dL	10.1 – 12.0 mg/dL	12.1 – 15.0 mg/dL	>15.0 mg/dL
Creatinine	1.1 - 1.5 x ULN	1.6 - 3.0 x ULN	3.1 - 6 x ULN	> 6 x ULN or dialysis required
ENZYMES				
	Grade 1	Grade 2	Grade 3	Grade 4
AST (SGOT)	1.25-2.5 × ULN	2.6 -5 × ULN	5.1-10 × ULN	>10 × ULN
ALT (SGPT)	1.25-2.5 × ULN	2.6- 5 × ULN	5.1-10 × ULN	>10 × ULN
GGT	1.25-2.5 × ULN	2.6-5 × ULN	5.1-10 × ULN	>10 × ULN
Alkaline Phosphatase	1.25-2.5 × ULN	1.6-5 × ULN	5.1-10 × ULN	>10 × ULN
Amylase	1.1-1.5 × ULN	1.6-2.0 × ULN	2.1-5.0 × ULN	>5.1 × ULN
Lipase	1.1-1.5 × ULN	1.6-2.0 × ULN	2.1-5.0 × ULN	>5.1 × ULN
URINALYSIS				
	Grade 1	Grade 2	Grade 3	Grade 4
Proteinuria	1+ or 200 mg - 1 g loss/day	2-3+ or 1-2 g loss/day	4+ or 2-3.5 g loss/day	nephrotic syndrome or >3.5 g loss/day
Hematuria	microscopic only <10 rbc/hpf	gross, no clots >10 rbc/hpf	gross, with or without clots, OR red blood cell casts	obstructive or required transfusion

CARDIOVASCULAR				
	Grade 1	Grade 2	Grade 3	Grade 4
Cardiac Rhythm		asymptomatic, transient signs, no Rx required	recurrent/persistent; symptomatic Rx required	unstable dysrhythmia; hospitalization and treatment required
Hypertension	transient increase >20 mm/Hg; no treatment	recurrent, chronic increase >20 mm/Hg. /treatment required	acute treatment required; outpatient treatment or hospitalization possible	end organ damage or hospitalization required
Hypotension	transient orthostatic hypotension with heart rate increased by <20 beat/min or decreased by <10 mm Hg systolic BP, No treatment required	symptoms due to orthostatic hypotension or BP decreased by <20 mm Hg systolic; correctable with oral fluid treatment	requires IV fluids; no hospitalization required	mean arterial pressure <60mm/ Hg or end organ damage or shock; requires hospitalization and vasopressor treatment
Pericarditis	minimal effusion	mild/moderate asymptomatic effusion, no treatment	symptomatic effusion; pain; ECG changes	tamponade; pericardiocentesis or surgery required
Hemorrhage, Blood Loss	microscopic/occult	mild, no transfusion	gross blood loss; 1-2 units transfused	massive blood loss; >3 units transfused
Electrocardiogram QT corrected interval prolonged		Average QTc 481 - 500 ms	Average QTc >= 501 ms; >60 ms change from baseline	Torsade de pointes; polymorphic ventricular tachycardia; signs/symptoms of serious arrhythmia
Sinus tachycardia	Asymptomatic, intervention not	Symptomatic; non-urgent	Supraventricular tachycardia	Symptomatic, urgent intervention indicated Life

---

indicated	medical intervention indicated Urgent medical intervention indicated	Asymptomatic, intervention not indicated Non-urgent medical intervention indicated -threatening consequences
-----------	---	---

---

RESPIRATORY				
	Grade 1	Grade 2	Grade 3	Grade 4
Cough	transient- no treatment	persistent cough; treatment responsive	Paroxysmal cough; uncontrolled with treatment	
Bronchospasm, Acute	transient; no treatment; 70% - 80% FEV 1 of peak flow	requires treatment; normalizes with bronchodilator; FEV 1 50% - 70% (of peak flow)	no normalization with bronchodilator; FEV 1 25% - 50% of peak flow; or retractions present	cyanosis: FEV 1 < 25% of peak flow or intubation necessary
Dyspnoea	dyspnoea on exertion	dyspnoea with normal activity	dyspnoea at rest	dyspnoea requiring Oxygen therapy
Adult respiratory distress syndrome	-	-	Present with radiologic findings; intubation not indicated	Life-threatening respiratory or hemodynamic compromise; intubation or urgent intervention indicated
Pulmonary hemorrhage	Mild symptoms; intervention not indicated	Moderate symptoms; invasive intervention not indicated	Transfusion indicated; invasive intervention indicated; hospitalization	Life-threatening consequences; intubation or urgent intervention indicated
Pneumonitis oxygen indicated	Asymptomatic; clinical or diagnostic observations only; intervention not indicated	Symptomatic; medical intervention indicated; limiting instrumental ADL	Severe symptoms; limiting self care ADL;	Life-threatening respiratory compromise; urgent intervention indicated (e.g., tracheotomy or intubation)
Lung infection -		Moderate symptoms; oral intervention indicated (e.g., antibiotic, antifungal, or antiviral)	IV antibiotic, antifungal, or antiviral intervention indicated; invasive intervention indicated	Life-threatening consequences; urgent intervention indicated

GASTROINTESTINAL				
	Grade 1	Grade 2	Grade 3	Grade 4
Nausea	mild or transient; maintains reasonable intake	moderate discomfort; intake decreased significantly; some activity limited	no significant intake; requires IV fluids	hospitalization required;
Vomiting	1 episode in 24 hours	2-5 episodes in 24 hours	>6 episodes in 24 hours or needing IV fluids	physiologic consequences requiring hospitalization or requiring parenteral nutrition
Constipation	requiring stool softener or dietary modification	requiring laxatives	obstipation requiring manual evacuation or enema	obstruction or toxic megacolon
Diarrhea	mild or transient; 3-4 loose stools/day or mild diarrhea last < 1 week	moderate or persistent; 5-7 loose stools/day or diarrhea lasting >1 week	>7 loose stools/day or bloody diarrhea; or orthostatic hypotension or electrolyte imbalance or >2L IV fluids required	hypotensive shock or physiologic consequences requiring hospitalization
Oral Discomfort/ Dysphagia	mild discomfort; no difficulty swallowing	some limits on eating/drinking	eating/talking very limited; unable to swallow solid foods	unable to drink fluids; requires IV fluids

NEUROLOGICAL				
	Grade 1	Grade 2	Grade 3	Grade 4
Neuro-Cerebellar	slight incoordination dysdiadochokinesis	intention tremor, dysmetria, slurred speech; nystagmus	locomotor ataxia	incapacitated
Psychiatric	mild anxiety or depression	moderate anxiety or depression; therapy required; change in normal routine	severe mood changes requiring therapy; or suicidal ideation; or aggressive ideation	acute psychosis requiring hospitalization; or suicidal gesture/attempt or hallucinations
Muscle Strength	subjective weakness / no objective symptoms/ signs	mild objective signs/symptoms/ no decrease in function	objective weakness function limited	paralysis
Paresthesia (burning, tingling, etc.)	mild discomfort; no treatment required	moderate discomfort; non-narcotic analgesia required	severe discomfort; or narcotic analgesia required with symptomatic improvement	incapacitating; or not responsive to narcotic analgesia
Neuro-sensory	mild impairment in sensation (decreased sensation, e.g., vibratory, pinprick, hot/cold in great toes) in focal area or symmetrical distribution; or change in taste, smell, vision and/or hearing	moderate impairment (mod decreased sensation, e.g., vibratory, pinprick, hot/cold to ankles) and/or joint position or mild impairment that is not symmetrical	severe impairment (decreased or loss of sensation to knees or wrists) or loss of sensation of at least mod degree in multiple different body areas (i.e., upper and lower extremities)	sensory loss involves limbs and trunk; paralysis; or seizures

MUSCULOSKELETAL				
	Grade 1	Grade 2	Grade 3	Grade 4
Arthralgia (joint pain)	mild pain not interfering with function	moderate pain, analgesics and/or pain interfering with function but not with activities of daily living	severe pain; pain and/or analgesics interfering with activities of daily living	disabling pain
Arthritis	mild pain with inflammation, erythema or joint swelling – but not interfering with function	moderate pain with inflammation, erythema or joint swelling – interfering with function, but not with activities of daily living	severe pain with inflammation, erythema or joint swelling –and interfering with activities of daily living	permanent and/or disabling joint destruction
Myalgia	myalgia with no limitation of activity	muscle tenderness (at other than injection site) or with moderate impairment of activity	severe muscle tenderness with marked impairment of activity	frank myonecrosis

SKIN				
	Grade 1	Grade 2	Grade 3	Grade 4
Mucocutaneous	erythema; pruritus	diffuse, maculo papular rash, dry desquamation	vesiculation or moist desquamation or ulceration	exfoliative dermatitis, mucous membrane involvement or erythema, multiforme or suspected Stevens-Johnson or necrosis requiring surgery
Induration	< 15 mm	15-30 mm	>30 mm	
Erythema	< 15 mm	15-30 mm	>30 mm	
Edema	< 15 mm	15-30 mm	>30 mm	
Rash at Injection Site	< 15 mm	15-30 mm	>30 mm	
Pruritus	slight itching at injection site	moderate itching at injection extremity	itching over entire body	

SYSTEMIC				
	Grade 1	Grade 2	Grade 3	Grade 4
Allergic Reaction	pruritus without rash	localized urticaria	generalized urticaria; angioedema	anaphylaxis
Headache	mild, no treatment required	transient, moderate; treatment required	severe; responds to initial narcotic therapy	intractable; requires repeated narcotic therapy
Fever: oral	37.5 - 38.5 C or 100.0 - 101.5 F	38.6 - 39.5 C or 101.6 - 102.9 F	39.6 - 40.5 C or 103 - 105 F	> 40 C or > 105 F
Fatigue	normal activity reduced < 48 hours	normal activity decreased 25-50% > 48 hours	normal activity decreased > 50% can't work	unable to care for self
Infections and infestations - Other,	Asymptomatic or mild symptoms; clinical or diagnostic observations only; intervention not indicated	Moderate; minimal, local or noninvasive intervention indicated; limiting age appropriate instrumental ADL	Severe or medically significant but not immediately life threatening; hospitalization or prolongation of existing hospitalization indicated; limiting self-care ADL	Life-threatening consequences; urgent intervention indicated
Sepsis	-	-	Blood culture positive with signs or symptoms; treatment indicated	Life-threatening consequences; urgent intervention indicated
Allergic reaction	Systemic intervention not indicated	Oral intervention indicated	Bronchospasm; hospitalization indicated for clinical sequelae; intravenous intervention indicated	Life-threatening consequences; urgent intervention indicated
Anaphylaxis	-	-	Symptomatic bronchospasm, with or without urticaria; parenteral intervention indicated; allergy-related	Life-threatening consequences; urgent intervention indicated

---

edema/angioede  
ma;  
hypotension

---

